### **Definitions:**

#### **Responses for MDS patients:**

**Complete Response (CR):** Bone marrow:  $\leq 5\%$  myeloblasts with normal maturation of all cell lines; persistent dysplasia will be noted. Peripheral blood:  $\text{Hgb} \geq 11 \text{ g/dL}$   $\text{Platelets} \geq 100 \times 10^9 / \text{L}$   $\text{Neutrophils} \geq 1.0 \times 10^9 / \text{L}$ ,  $\text{Blasts} 0\%$

**Partial response (PR):** All CR criteria if abnormal before treatment except: bone marrow blasts decreased by  $\geq 50\%$  over pretreatment but still  $> 5\%$

**Marrow CR:** Blasts  $\leq 5\%$  and decrease by  $\geq 50\%$  from baseline (baseline blasts should be above 5% to be eligible for marrow CR)

**Hematologic Improvement (HI):** (responses must last at least 8 weeks) **Erythroid response** [HI-E; (if pretreatment  $\text{Hgb} < 11 \text{ g/dL}$ )]:  $\text{Hgb}$  increase by  $\geq 1.5 \text{ g/dL}$ ; Relevant reduction of units of RBC transfusions by an absolute number of at least 4 RBC transfusions/8 weeks compared with the pretreatment transfusion number in the previous 8 weeks. Only RBC transfusions given for an  $\text{Hgb}$  of  $\leq 9.0 \text{ g/dL}$  pretreatment will count in the RBC transfusion response evaluation.

**Platelet response** [HI-P; ((if pretreatment Platelet count  $< 100 \times 10^9 / \text{L}$ )]: Absolute increase of  $\geq 30 \times 10^9 / \text{L}$  for patients starting with  $> 20 \times 10^9 / \text{L}$  platelets, or increase from  $< 20 \times 10^9 / \text{L}$  to  $> 20 \times 10^9 / \text{L}$  and by at least 100%.

**Neutrophil response** [HI-N; (pretreatment,  $\text{ANC} < 1.0 \times 10^9 / \text{L}$ )]: At least 100% increase and an absolute increase  $> 0.5 \times 10^9 / \text{L}$

**Progression/Relapse after hematological improvement:**  $\geq 1$  of the following:  $\geq 50\%$  decrement from maximum response levels in granulocytes or platelets;  $\downarrow$  in Hgb by  $\geq 1.5$  g/dL; transfusion dependence

**Stable Disease:** Not satisfying criteria for Complete Remission, Partial Response, Marrow CR, Hematologic Improvement or Progression/Relapse.

**Responses for AML patients:**

**Complete Response (CR):** Bone marrow:  $\leq 5\%$  myeloblasts with normal maturation of all cell lines, ANC  $>/= 1.0 \times 10^9/L$ , platelet count  $>/= 100 \times 10^9/L$ , no detectable Auer rods and no extramedullary leukemia.

**Complete Response (CR) with incomplete hematologic recovery (CRI):** Responses as in CR but ANC  $< 1.0 \times 10^9/L$ .

**Complete Response (CR) with incomplete platelets recovery (CRp):** Responses as in CR but platelets  $< 100 \times 10^9/L$ .

**Partial response (PR):** All CR criteria if abnormal before treatment except: bone marrow blasts decreased by  $\geq 50\%$  over pretreatment but still  $> 5\%$ .

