Treatment with AZA and DAC improves cyopenias and prolongs survival in patients with MDS, though only 30-40% of patients respond to therapy. Azacitidine was approved in USA based on phase III clinical trial that compared azacitidine to best supportive care. Overall response rate to azacitidine was 34% with significant delay in AML transformation but no overall survival benefit. In a phase III clinical trial conducted in Europe, azacitidine was compared to conventional care arm that included best supportive care, low dose cytarabine, and intensive chemotherapy. The median OS for patients treated with azacitidine was 24.5 months compared to 15 months for patients treated with best supportive care (HR .58, p = .00001).

Studies have shown that MDS patients with *TET2* mutations have a higher response rate to AZA. In a study of 82 patients with MDS and oligoblastic AML (20-30% BM blasts) treated with AZA, *TET2* mutations were found in 15% of the patients. Patients with *TET2* mutations had a higher response to AZA compared to wild type patients (82% vs 45%, p = 0.04, respectively). In a larger retrospective study, samples from 213 patients with MDS were sequenced prior to their treatment with hypomethylating agents (HMAs) for the presence of 40 recurrent gene mutations. *TET2* mutations with variant allelic frequency (VAF) >10% were associated with a significantly higher overall response rate (ORR) compared with WT (60% vs. 43%; OR, 1.99;

95%CI, 1.05-3.80,  $P=0.036$ ). Further, mice with transplanted TET2-null hematopoietic cells exhibit decrease in white blood counts when they are treated with AZA compared to vehicle.

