#### Response Criteria for extended treatment eligibility

- complete remission, partial remission, or hematologic improvement (CR/PR/HI) per IWG 2006 criteria for patients with MDS
- (CR/PR/marrow CR) per IWG 2003 criteria for patients with AML
- If the response is stable disease and the investigator determines the patient is gaining clinical benefit, patient may continue on treatment until progression.

At the point in which the patient meets the any EOT criteria (Section 6) the patient will enter into the follow up period to follow for survival status. The patient will be followed for up to 1 year and/or death, whichever were to occur first. End of study (EOS) is defined as the time the patient completes 1 year of survival follow up and/or patient's death, whichever were to occur first.

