## **12.0 MEASUREMENT OF EFFECT**

The response criteria recommended by the MDS International Working Group 2006. Responses must be verified, documented, and signed at cycle 6 in the local medical record by the local PI. (Patients are considered non evaluable if they have received less than 2 courses of treatment, unless there is clear disease progression.)

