### **14.0 STATISTICAL CONSIDERATIONS**

**Definition of primary outcome/endpoint:** A binary indicator of overall response, defined as achieving CR, PR, or HI) per 2006 IWG criteria for MDS and MDS/MPN overlap and (CR, CRp, CRi, or PR) per 2003 IWG criteria for AML after 6 cycles of treatment

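### As written, the AML categories leave out a cleared marrow with both neutrophils and platelets low, so that patient counts as a non-responder in the primary ORR

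*Combined protocol and SAP*

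**What the plan says.** Section 12.0 (Responses for AML patients) sets CR as marrow blasts of at most 5% with normal maturation, ANC at least 1.0 × 10⁹/L, platelets at least 100 × 10⁹/L, "no detectable Auer rods and no extramedullary leukemia". The other three categories are built on CR:

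- CRi: "Responses as in CR but ANC" below 1.0 × 10⁹/L.
- CRp: "Responses as in CR but platelets" below 100 × 10⁹/L.
- PR: "All CR criteria if abnormal before treatment except: bone marrow blasts decreased by" at least 50% from pretreatment, with blasts remaining above 5%. No upper limit on residual blasts is given, and the text is the same as the MDS PR text.

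The primary endpoint in Section 14.0 counts "CR, CRp, CRi, or PR) per 2003 IWG criteria for AML after 6 cycles of treatment".

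Two other places bear on the same categories. Section 12.0 opens by naming only one source: "The response criteria recommended by the MDS International Working Group 2006". Section 3.2 and Appendix V decide extended treatment for AML on "CR/PR/marrow CR) per IWG 2003 criteria for patients with AML", yet Section 12.0 defines marrow CR only for MDS, and Section 14.0 does not count it.

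**The concern.** CR, CRp, CRi and PR are the whole AML part of the primary endpoint, so a patient who fits none of them lowers the ORR. CRi and CRp each change one count criterion. Neither covers a patient in whom both counts are low.

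The state is foreseeable from the protocol itself. Section 1.2 describes leukopenia and thrombocytopenia as common with azacitidine. Section 7.0 gives the second course whatever the degree of myelosuppression and allows no dose modification. Section 4 admits relapsed or refractory AML and blast-phase MPN.

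PR adds an internal inconsistency, because it applies the CR count limits only where the count was abnormal at entry. With identical counts at cycle 6, a patient with leukemia still in the marrow may be scored a responder while a patient whose marrow has cleared is not. The trial is open-label and single-arm, responses are signed off by the local PI, and no independent adjudication is described. Two assessors could therefore score the same patient differently.

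**Working it through.** **1. Literal scoring of Section 12.0.** Take illustrative AML patients with entry blasts of 80% and cycle 6 values of ANC 0.7 and platelets 60 (× 10⁹/L). Assume no Auer rods or extramedullary disease, and that the maturation criterion is met or was not abnormal at entry.

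| Entry counts | Cycle 6 blasts | CR | CRi (platelets ≥100 still needed) | CRp (ANC ≥1.0 still needed) | PR (blasts >5%, fall ≥50%) | Counted in ORR |
|---|---|---|---|---|---|---|
| Both adequate | 3% or 5% | no | no | no | no, blasts not >5% | no |
| Both adequate | 6%, 10% or 40% | no | no | no | yes | yes |
| Both low | 3% or 5% | no | no | no | no | no |
| Both low | 6%, 10% or 40% | no | no | no | no, counts not recovered | no |

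The gap (rows 1 and 3) does not depend on entry counts. The reversal (row 1 against row 2) does. If either count was abnormal at entry and is still low, PR fails as well. The reversal therefore needs both counts to have been adequate at entry.

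**2. Weight of one patient.** One reclassified patient is 1/28 = 3.6 percentage points of the final ORR and 1/12 = 8.3 points at stage 1. Section 14.0 stops the trial at 3 or fewer responses in 12 and rejects the null at 11 or more in 28. One patient can therefore separate 3 from 4 of 12, or 10 from 11 of 28.

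**3. The plan's operating characteristics, and an illustration.** For the written rule,

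P(reject) = Σ over x = 4 to 12 of P(Bin(12, p) = x) × P(Bin(16, p) ≥ 11 − x).

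This gives 0.169 at p = 0.3 and 0.868 at p = 0.5, against the stated 0.1 and 0.8. Rejecting at 12 or more gives 0.095 and 0.802. That mismatch is a separate matter; the written rule is used below only as a baseline.

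Suppose the response rate with gap patients counted is 0.5, and a share d of all patients falls in the gap. The counted rate is then 0.5 − d. The values of d are assumptions, since the documents give none.

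| d | P(stop at stage 1) | P(reject) |
|---|---|---|
| 0 | 0.073 | 0.868 |
| 1/28 = 0.036 | 0.114 | 0.780 |
| 0.05 | 0.135 | 0.737 |
| 0.10 | 0.225 | 0.551 |

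This shows sensitivity only. It is not an estimate of the effect in this trial.

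**The case against.** The strongest reply is that the name of CRi, which speaks of incomplete recovery of blood counts in general, invites an assessor to include a patient with both counts low. The name does favor that reading and supports the fix. But the written criterion beneath it names only the ANC, and a label does not override a stated threshold.

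A second reply is that marrow CR, accepted for AML in Section 3.2 and Appendix V, would cover the cleared marrow. It does not help the ORR: Section 14.0 does not count it, and Section 12.0 defines it only for MDS.

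A reader might go further and infer that PR is also wrong. A fall from 80% to 40% meets the blast rule, while Section 1.1 speaks of "oligoblastic AML (20-30% BM blasts"), so the ORR might seem mis-scored in both directions. The documents do not support that. Section 14.0 names the IWG 2003 criteria, which are not reproduced, so an uncapped PR cannot be shown to be a misclassification. Sharing the MDS wording does not prove an error either. The route is also narrow: every other CR criterion abnormal at entry (counts, maturation, Auer rods, extramedullary disease) must be met.

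It is also fair to object that no frequency can be given. Neither the number of AML patients nor the rate of double cytopenia with a cleared marrow is stated, so any count of affected patients would be guesswork.

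**Conclusion.** The point holds for CRi and CRp. On the written criteria, an AML patient with blasts of 5% or less and both ANC below 1.0 and platelets below 100 is a non-responder in the primary analysis. If both entry counts were adequate, the same patient with residual blasts above 5% could be a PR, subject to the other PR conditions. This is a stated rule that orders outcomes inconsistently, not merely missing detail.

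Each affected patient is worth 3.6 points of the final ORR, or 8.3 points at stage 1, and could change either decision. The total effect cannot be computed. The gap by itself can only lower the counted ORR. A net bias for the whole AML definition has no established sign, because whether PR is too generous cannot be judged from the documents. The conclusion rests on reading the criteria literally and on no outside source.

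**What to change.** In Section 12.0, define AML CRi as all CR criteria met except ANC below 1.0 × 10⁹/L and/or platelets below 100 × 10⁹/L, and make CRp the subset in which only platelets are low. Apply this before the stage 1 responses are counted.

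In the same amendment:

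- Reconcile the criteria source (IWG 2006 in the opening of Section 12.0, IWG 2003 for AML in Sections 3.2 and 14.0 and Appendix V) and the AML category lists. Either define AML marrow CR or remove it, and say how it relates to the ORR.
- Have the sponsor confirm whether the AML PR text, including the absence of a residual-blast limit, matches the IWG 2003 criteria that Section 14.0 names. No specific limit is proposed here.

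The cost is a small wording amendment. ANC, platelets and marrow blasts are already collected (Appendix VI). A few more patients may count as responders. Section 6.4 ties end of treatment to response as defined in Section 12.0, and Section 3.2 ties extended treatment to response categories. The sponsor should check these passages for consistency with the revised definition; no treatment rule is suggested.

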## **13.0 DATA REPORTING / REGULATORY CONSIDERATIONS**

Adverse event lists, guidelines, and instructions for AE reporting can be found in Section 8.0 (Adverse Events: List and Reporting Requirements).

### **13.1 Data Reporting**

The OnCore™ Database will be utilized, as required by the Case Comprehensive Cancer Center, to provide data collection for both accrual entry and trial data management. OnCore™ is a Clinical Trials Management System housed on secure servers maintained at Case Western Reserve University. OnCore™. Access to data through OnCore™ is restricted by user accounts and assigned roles. Once logged into the OnCore™ system with a user ID and password,

OnCore™ defines roles for each user which limits access to appropriate data. User information and password can be obtained by contacting the OnCore™ Administrator at [[contact]](mailto:[contact]). OnCore™ is designed with the capability for study setup, activation, tracking, reporting, data monitoring and review, and eligibility verification. This study will utilize electronic Case Report Form completion in the OnCore™ database. A calendar of events and required forms are available in OnCore™.

## 13.2 Regulatory Considerations

The study will be conducted in compliance with ICH guidelines and with all applicable federal (including 21 CFR parts 56 & 50), state or local laws.

### 13.2.1 Written Informed consent

Provision of written informed consent must be obtained prior to any study-related procedures. The Principal Investigator will ensure that the subject is given full and adequate oral and written information about the nature, purpose, possible risks and benefits of the study as well as the subject's financial responsibility. Subjects must also be notified that they are free to discontinue from the study at any time. The subject should be given the opportunity to ask questions and be allowed time to consider the information provided.

The original, signed written Informed Consent Form must be kept with the Research Chart in conformance with the institution's standard operating procedures. A copy of the signed written Informed Consent Form must be given to the subject. Additionally, documentation of the consenting process should be located in the research chart.

### 13.2.2 Subject Data Protection

In accordance with the Health Information Portability and Accountability Act (HIPAA), a subject must sign an authorization to release medical information to the sponsor and/or allow the sponsor, a regulatory authority, or Institutional Review Board access to subject's medical information that includes all hospital records relevant to the study, including subjects' medical history.

### 13.2.3 Retention of records

The Principal Investigator of The Case Comprehensive Cancer Center supervises the retention of all documentation of adverse events, records of study drug receipt and dispensation, and all IRB correspondence for as long as needed to comply with local, national and international regulations. No records will be destroyed until the Principal Investigator confirms destruction is permitted.

#### **13.2.4 Audits and inspections**

Authorized representatives of the sponsor, a regulatory authority, an Independent Ethics Committee (IEC) or an Institutional Review Board (IRB) may visit the site to perform audits or inspections, including source data verification. The purpose of an audit or inspection is to systematically and independently examine all study-related activities and documents to determine whether these activities were conducted, and data were recorded, analysed, and accurately reported according to the protocol, Good Clinical Practice (GCP), guidelines of the International Conference on Harmonization (ICH), and any applicable regulatory requirements. For multi-center studies, participating sites must inform the sponsor-investigator of pending audits.

### **14.0 STATISTICAL CONSIDERATIONS**

**Definition of primary outcome/endpoint:** A binary indicator of overall response, defined as achieving CR, PR, or HI) per 2006 IWG criteria for MDS and MDS/MPN overlap and (CR, CRp, CRi, or PR) per 2003 IWG criteria for AML after 6 cycles of treatment

**Definition of secondary outcomes/endpoints:**

1. Incidence of adverse events of the combination defined by CTCAE 4.1 criteria.  
Toxicity will be any drug related Grade 3 or 4 toxicity.
2. Response duration to the combination recorded from start of treatment to progression
3. Overall survival measured from start of treatment to death or last follow up

**Sample size justification and study design:** The study sample size was determined using Minimax Simon's two-stage design (Simon, 1989. The null hypothesis that the true response rate is 0.3 will be tested against a one-sided alternative that the true response rate is 0.5. In the first stage, 12 patients will be accrued. If there are 3 or fewer responses, the study will be stopped. Otherwise, 16 additional patients will be accrued for a total of 28. The null hypothesis will be

rejected if 11 or more responses are observed in 28 patients. This design yields a type I error rate of 0.1 and a power of 0.8 when the true response rate is 0.5.

**Analysis plan:** Descriptive statistics will be used for the primary endpoint and secondary endpoints 1,2, and 3. Overall survival will be estimated with Kaplan Meier method and will be compared to the survival of a historical cohort of MDS patients treated at our institution with single agent Azacitidine between 2006-2012 using a one-sample log rank test. A Cochran-Mantel-Haenszel test will be used to test for differences in response rate by mutational status controlling for treatment. Unadjusted and adjusted logistic regression models were used to predict response to therapy. Models will be adjusted for covariates including age, sex, and other prognostic factors. The odds ratio (OR) and 95% confidence intervals (CI) will be estimated for the risk group (mutated) and compared with the reference group (WT).

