### **8.2.3 Adverse Event Evaluation**

The investigator or designee is responsible for ensuring that all adverse events (both serious and non-serious) observed by the clinical team or reported by the subject, which occur after the

subject has signed the informed consent are fully recorded in the subject's medical records. Source documentation must be available to support all adverse events.

The investigator or sub-investigator (treating physician if applicable) or delegated staff will provide the following for all adverse events (both serious and non-serious):

- Event term (as per CTCAE 4.1)
- Description of the event
- Date of onset and resolution
- **Expectedness of the toxicity**
- **Grade of toxicity**
- **Attribution of relatedness to the investigational agent- (this must be assigned by an investigator, sub-investigator, or treating physician)**
- Action taken as a result of the event, including but not limited to; no changes, dose interrupted, reduced, discontinued, etc. or action taken with regard to the event, i.e. no action, received conmed or other intervention, etc.
- Outcome of event

**An expected adverse event** is an event previously known or anticipated to result from participation in the research study or any underlying disease, disorder, or condition of the subject. The event is usually listed in the Investigator Brochure, consent form or research protocol.

**An unexpected adverse event** is an adverse event not previously known or anticipated to result from the research study or any underlying disease, disorder, or condition of the subject.

**Attribution** is the relationship between an adverse event or serious adverse event and the study drug. Attribution of any adverse event can only be assessed by the PI and/or Co-I. Attribution will be assigned as follows:

- Definite – The AE is clearly related to the study drug.
- Probable – The AE is likely related to the study drug.
- Possible – The AE may be related to the study drug.
- Unlikely – The AE is doubtfully related to the study drug.
- Unrelated – The AE is clearly NOT related to the study drug.

Protocol must specify if attribution is required for individual components of the treatment regimen or the treatment regimen as a whole.

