### **8.4 Reporting Procedures for Serious Adverse Events**

For the purposes of safety reporting, all adverse events will be reported that occur during treatment and through 30 days after the final dose of study drug. Adverse events, both serious and non-serious, and deaths that occur during this period will be recorded in the source documents. All SAEs should be monitored until they are resolved or are clearly determined to be due to a subject's stable or chronic condition or intercurrent illness(es). Related AEs will be followed until resolution to baseline or grade 1 or stabilization.

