#### **Treatment Period (Day -3 to C6D28)**

1. Hematology exams (Appendix VI) at the start of each cycle (day 1) and the last day of cycle 6 (C6D28)
2. Serum Chemistry (Appendix VI), including Creatinine, bilirubin, ALT or AST at the start of each cycle (day 1)
3. Bone marrow aspirate and/or biopsy to confirm response, to be performed at the end of cycle 6. 10 ML of whole blood or bone marrow aspirate whichever available will be collected in extra lab tube. All bone marrows samples are to be stored at Cleveland Clinic
4. Conventional cytogenetics to be performed at the end of cycle 6
5. Documentation of frequency of transfusions (only PRBC and Platelets) prior to start of each new cycle.
6. Documentation in the medical record of any grade 2 or higher adverse events at each visit. For guidelines on SAE Reporting and AE entry for Case Report
7. Documentation of any prior administration of growth factors and ESA prior to start of each cycle
8. A 10 ML blood sample that will be used for next generation targeted deep sequencing of genes that are common in myeloid malignancies

9. Physical exam and ECOG performance status occurring at the end of each cycle
10. Vital signs occulting at each visit
11. Pregnancy test if applicable
12. MDS Response Assessment, assessed by the treating physician occurring at the end of cycle 6 or EOT, whichever occurs first.
13. Methylation panel only occurring in Cycle 1
14. Azacitidine will be administered intravenously or subcutaneously at a fixed dose of 75mg/m^2/day for 7 consecutive days, (allowing interruptions for weekends, and holidays, of each 28-day cycle).
15. Ascorbic acid will be administered orally daily at 1 g/day three days prior to start azacitidine and then continues daily for a total of 28 days of each 28 days cycle.

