#### **Extended Treatment Period (Cycles 7+)**

1. Documentation of frequency of transfusions (only PRBC and Platelets) prior to start of each new cycle
2. Documentation in the medical record of any grade 3 or higher adverse events at each visit. For guidelines on SAE Reporting and AE entry for Case Report
3. Physical exams and ECOG performance status occurring at the end of each cycle
4. Vital Signs at each visit
5. Hematology exams (Appendix VI) at the start of each cycle (day 1)
6. Serum Chemistry (Appendix VI), including Creatinine, bilirubin, ALT or AST at the start of each cycle (day 1).
7. Azacitidine will be administered intravenously or subcutaneously at a fixed dose of 75mg/m^2/day for 7 consecutive days, (allowing interruptions for weekends, and holidays)

of each 28-day cycle

8. Ascorbic acid will be administered orally daily at 1 g/day for a total of 28 days of each 28 days cycle.

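### Toxicity is defined as drug-related Grade 3 or 4 only, so a fatal drug-related event falls outside the toxicity count; separately, Sections 8 and 11.1 disagree on which adverse events below Grade 3 are captured

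*Combined protocol and SAP*

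**What the plan says.** Safety is the first secondary objective (Section 2.2). Section 14.0 turns it into an endpoint in two sentences. The first sets no grade limit: "Incidence of adverse events of the combination defined by CTCAE 4.1 criteria". The second defines a narrower measure: "Toxicity will be any drug related Grade 3 or 4 toxicity". The analysis plan in the same section says only that "Descriptive statistics will be used for the primary endpoint and secondary endpoints 1,2, and 3".

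On recording, Section 11.1 gives different floors by period:

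- Treatment Period (to the end of cycle 6): "Documentation in the medical record of any grade 2 or higher adverse events at each visit".
- Extended Treatment Period (cycle 7 onward): "Documentation in the medical record of any grade 3 or higher adverse events at each visit". The End of Treatment list carries the same Grade 3 floor.

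Section 8 has no floor. Section 8.2.3 makes the investigator or designee "responsible for ensuring that all adverse events (both serious and non-serious) observed by the clinical team or reported by the subject", and adds that events occurring after the "subject has signed the informed consent are fully recorded in the subject's medical records". Section 8.4 says "all adverse events will be reported that occur during treatment and through 30 days after the final dose of study drug".

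**The concern.** A toxicity summary is normally read as the share of patients with a severe treatment-related event. A definition that stops at Grade 4 leaves out the most severe outcome. Taken literally, a patient who dies of a drug-related event, with no separate drug-related Grade 3 or 4 event on record, sits in the group without toxicity.

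The recording rules raise a different question. An endpoint worded as adverse-event incidence, with no grade limit, needs one capture rule throughout. If staff follow Section 11.1 in one place and Section 8 in another, the incidence of lower-grade events will partly reflect which rule was applied.

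**Working it through.** **Step 1. Does any other text bring fatal events into the toxicity definition?** The places where a fatal event or a toxicity grade range appears are:

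| Place | What it does with a fatal event |
|---|---|
| 14.0, endpoint 1, first sentence | Counts it: no upper grade limit on adverse-event incidence |
| 14.0, endpoint 1, second sentence | Does not name it: range is Grade 3 or 4 |
| 14.0, overall survival | Counts it, whatever the cause |
| 8.2.2 | Classes it as a serious adverse event |
| 8.4 | Has it recorded in source documents to 30 days after the last dose |
| 6.4, Table 1 | Uses the same Grade 3 or 4 range for toxicity and lists death as a separate item |

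Nothing widens the second sentence. Table 1 points the other way, because it treats death as something apart from a Grade 3 or 4 event. The documents do not state which grade a fatal event carries; this reading assumes it is graded above 4.

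**Step 2. Size per patient.** The plan gives no expected toxicity rate, precision or safety denominator, so there is no stated figure to reproduce. The planned sample size is 28 (Section 3.1).

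- Shift in the toxicity proportion = k/N, where k is the number of patients whose only severe drug-related event is fatal.
- N = 28, k = 1: 1/28 = 3.6 percentage points.
- N = 28, k = 2: 2/28 = 7.1 percentage points.
- If accrual ended after the 12 first-stage patients (Section 14.0), k = 1: 1/12 = 8.3 percentage points.

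For scale, the exact (Clopper-Pearson) 95% interval is 0% to 12.3% for 0 of 28, 0.1% to 18.3% for 1 of 28, and 0.9% to 23.5% for 2 of 28. A shift of one patient lies well within the sampling uncertainty of the estimate, but it always goes downward.

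**Step 3. Which grades are certain to be captured?** Set the Section 11.1 floors against Sections 8.2.3 and 8.4:

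| Grade | Cycles 1-6 under 11.1 | Cycle 7+ and end of treatment under 11.1 | Under 8.2.3 and 8.4 |
|---|---|---|---|
| 1 | Not required | Not required | Required |
| 2 | Required | Not required | Required |
| 3 and above | Required | Required | Required |

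The sections disagree on Grade 1 in every period and on Grade 2 after cycle 6 and at end of treatment. They agree on Grade 3 and above throughout. The difference cannot be explained as source record versus case report form, because Sections 8.2.3 and 11.1 both speak of the medical record. The two Section 11.1 floors can even meet at one visit: footnote G of the calendar (Section 11.2) lets the last visit of cycle 6 serve as the end-of-treatment visit.

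**The case against.** The strongest reply is that no safety information is lost. The first sentence of the endpoint has no grade ceiling, and deaths are also captured as serious adverse events and in overall survival. This stands. A reader might infer that drug-related deaths vanish from the safety results, or that the trial's conclusion is biased. The documents support neither: the death is left out of one summary measure only, and that measure has no test, threshold or stopping boundary. What remains is that overall survival does not separate drug-related deaths from others, and serious adverse event reporting does not put the patient into the toxicity count.

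A second reply is that the pattern may never occur. Section 8.1.1 lists low blood cell counts among the common effects of azacitidine, so a patient who dies of a drug-related event may well have a qualifying Grade 3 or 4 event already. This also stands. The documents give no grade-specific rates, so the number of affected patients cannot be estimated and may be zero.

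On recording, a reader might infer that Grade 2 recording stops after cycle 6, so that its incidence falls towards zero. The documents do not support that. Sections 8.2.3 and 8.4 still ask for all adverse events, and the calendar shows adverse-event recording as a continuous row. The text shows a conflict and uncertain capture, not a known loss. A lighter floor in extended treatment may also be deliberate, and Section 14.0 plans no comparison of Grade 2 incidence between periods.

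**Conclusion.** The definition should be corrected. As written, it leaves a patient whose only severe drug-related event is fatal out of the toxicity count, at 3.6 percentage points per patient if all 28 form the denominator. This rests on three assumptions: that denominator, a fatal event being graded above 4, and no other drug-related Grade 3 or 4 event in the same patient. The frequency is unknown and no decision depends on the result, so this is a defect of definition and reporting, not a threat to the trial.

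The capture conflict is real but secondary. It makes all-grade incidence unreliable for Grade 1 events in every period and for Grade 2 events after cycle 6 and at end of treatment. It does not touch the count of Grade 3 or higher events.

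**What to change.** In Section 14.0, replace the second sentence of secondary endpoint 1 with: *Toxicity will be any drug-related event of Grade 3 or higher, including fatal events.* Add that drug-related deaths will also be listed separately, and name the denominator (for example, all patients who received study drug).

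For recording, do one of the following:

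1. State one capture threshold for all periods in Section 11.1 (Treatment Period, Extended Treatment Period and End of Treatment), and align Sections 8.2.3 and 8.4 with it. Editing Section 11.1 alone would leave the conflict with Section 8 in place unless the threshold chosen is all grades.
2. Limit the reported adverse-event incidence to Grade 3 or higher, which every section already captures, and say so in Section 14.0.

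The change to the toxicity definition costs a sentence and may raise the reported proportion slightly. The first recording option adds some adverse-event entry, mainly after cycle 6, and more if Grade 1 is included. The second adds no data entry but gives up a summary of lower-grade events. Neither changes treatment, visits or sample size. The recording choice is best made early, because events that were not recorded may not be recoverable at analysis.
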